Appendix K Abbreviations

Abbreviation or special term	Explanation
AE	adverse event
ALP	alkaline phosphatise
ALT	alanine aminotransferase
AML	acute myeloid leukaemia
ANC	absolute neutrophil count
AST	aspartate aminotransferase
ATM	ataxia telangiectasia mutated
ATR	ataxia telangiectasia and Rad3-related protein
AUC	area under the curve
CCI	CCI
BRCAm	breast cancer gene 1 and 2 mutations
САР	College of American Pathologists
CI	confidence interval
CLIA	Clinical Laboratory Improvement Amendments
C _{max}	maximum plasma concentration
C _{min,ss}	minimum plasma concentration at steady state
COVID-19	coronavirus disease 2019
CR	complete response
CrCl	creatinine clearance
CRF	case report form (electronic/paper)
CSP	clinical study protocol
CSR	clinical study report
CT	computed tomography
CCI	CCI
CTCAE	common terminology criteria for adverse event
CCI	CCI
CYP3A4	cytochrome P450 3A4
DCO	data cut-off
DDR	DNA damage response agent
DLT	dose-limiting toxicity
DNA	deoxyribonucleic acid
DNA-PK	DNA-dependent protein kinase
DNA-PKcs	DNA-dependent protein kinase catalytic subunit

Abbreviation or special term	Explanation		
DSB	double-strand break		
ECG	electrocardiogram		
ЕСНО	echocardiogram		
ECOG PS	Eastern Cooperative Oncology Group performance status		
EDTA	ethylenediaminetetraacetic acid		
FDA	food and drug administration		
FFPE	formalin-fixed paraffin embedded		
FTIH	first time in human		
gBRCA m	germline breast cancer gene 1 and 2 mutations		
GCP	good clinical practice		
G-CSF	granulocyte colony-stimulating factor		
GI	gastrointestinal		
НСР	Health Care Professional		
HNSTD	highest non-severely toxic dose		
h	hour		
HR	homologous recombination		
CCI	CCI		
HL	Hy's Law		
IB	Investigator's brochure		
ICF	informed consent form		
ICH	international conference on harmonisation		
IEC	independent ethics committee		
INR	international normalised ratio		
IRB	institutional review board		
IV	intravenously		
MBAD	minimum biologically active dose		
MDS	myelodysplastic syndrome		
MedDRA	medical dictionary for regulatory activities		
MFD	maximum feasible dose		
Min	minute		
mPFS	median progression-free survival		
mRECIST	modified response evaluation criteria in solid tumours (RECIST) 1.1		
MRI	magnetic resonance imaging		
MTD	maximum tolerated dose		
MUGA	MUltiGated Angiography		

Abbreviation or special term	Explanation	
NA	not applicable	
NE	not evaluable	
NHEJ	non-homologous end joining	
NOACs	new oral anticoagulants	
NTL	non-target lesions	
ORR	objective response rate	

Edition Number 4.0

Date 21 January 2022

4.2.5	Exploratory research variables	61
5	INTERIM ANALYSES	61
6	CHANGES OF ANALYSIS FROM PROTOCOL	61
7	REFERENCES	62

LIST OF ABBREVIATIONS

Abbreviation or special term*	Explanation
AE	Adverse event
Ae(t1-t2)	Amount of drug excreted unchanged into urine from time t1 to t2.
AUC	Area under the plasma concentration time curve
AUCinf	Area under the plasma concentration time curve from time zero to infinity.
AUC τ	Area under the plasma concentration time curve in the dose interval
AUC(0-12)	Area under the plasma concentration-time curve from time zero to 12 hours post-dose.
AUC(0-24)	Area under the plasma concentration-time curve from time zero to 24 hours post-dose.
AUClast	Area under the plasma concentration-time curve from time zero to last quantifiable concentration.
AUCextr	Extrapolated area under the curve from tlast to infinity, expressed as percentage of AUCinf
BoR	best objective response
Cavg	Average drug concentration over a dosing interval
CI	confidence interval
Cmax	Maximum observed plasma (peak) drug concentration
Ctrough	Lowest observed plasma (trough) drug concentration reached before the next dose is administered.
CL/F	Apparent total body clearance of drug from plasma after extravascular administration.
CLR	Renal clearance of drug from plasma
CR	Complete response
CrCL	Creatinine clearance
CSP	Clinical study protocol
CSR	Clinical study report
CCI	CCI
CTCAE	Common Terminology Criteria for Adverse Event
CCI	CCI
CV	Coefficient of variation

Abbreviation or special term*	Explanation
DCO	Data cut-off
DLT	Dose-limiting toxicity
DoR	Duration of response
eCRF	Electronic Case Report Form
ECG	Electrocardiogram
ECHO	Echocardiogram
ECOG PS	Eastern Cooperative Oncology Group Performance Status
fe(t1-t2)	Percentage of dose excreted unchanged in urine from time t1 to time t2
GI	Gastrointestinal
GPS	Global product statistician
gSD	Geometric standard deviation
h	Hour
HR	Homologous recombination
HRR _m	Homologous recombination repair mutation
IPD	Important protocol deviations
MedDRA	Medical Dictionary for Regulatory Activities
MRT _{inf}	Mean residence time of the unchanged drug in the systemic circulation
NA	Not applicable
NC	Not Calculated
NE	Not evaluable
NPD	Non progressive disease
NTL	Non target lesion
NQ	Not quantifiable
OS	Overall survival
PD	Progressive disease
PD _c	Pharmacodynamic
PFS	Progression-free survival
PK	Pharmacokinetic(s)
PLD	Pegylated liposomal doxorubicin
PR	Partial response

Abbreviation or special term*	Explanation
QTc	Corrected QT interval
Rac	Accumulation ratio
RDI	Relative dose intensity
RECIST	Response Evaluation Criteria in Solid Tumours
Rsq adj	Statistical measure of fit for the regression used for λz determination adjusted for the number of used data points ($\lambda z N$)
SAP	Statistical analysis plan
SD	Stable disease in RECIST assessments / Standard deviation in statistical summaries
t	Time
TCP	Temporal change parameter in systemic exposure
TL	Target lesion
$t_{1/2\lambda z}$	Half-life associated with terminal slope (λz) of a semi-logarithmic concentration-time curve
t_{last}	Time of last observed (quantifiable) concentration
t_{max}	Time to reach peak or maximum observed concentration or response following drug administration
t_{sm}	Tumour size measurement
ULN	Upper limit normal
V_{ss}/F	Volume of distribution (apparent) at steady state following extravascular administration
V_z/F	Volume of distribution (apparent) following extravascular administration (based on terminal phase)
τ	Dose interval (tau)
λz	Terminal elimination rate constant
λz lower	Lower (earlier) t used for λz determination
λz upper	Upper (later) t used for λz determination
$\lambda z N$	Number of data points used for λz determination
λz span ratio	Time period over which λz was determined as ratio of $t_{1/2\lambda z}$

*The PK abbreviations and definitions are updated from those in the CSP in line with current AZ guidance for PK reporting

VERSION HISTORY

Version 1.0, 16 September 2019

New document.

Version 2.0, 25 June 2021

Section 1.0

A new section 1.1 added with brief introduction to the study and the list of documents on which this statistical analysis plan is based.

A new section 1.2 added to list out available modules of the study as per latest protocol amendment.

Within Table 1 Corrected the spelling 'pharamcodynamic' to 'pharmacodynamic'

Added that AUC_{0-t} and C_{max} ratio for food effect is only applicable to food effect cohort in the monotherapy expansion phase.

Added that Post-dose to pre-dose 4 β -hydroxy cholesterol ratio is only applicable to monotherapy cohorts.

A footnote a is added.

Section 2.1 New section added.

A paragraph added to briefly explain how the data will be analysed and CSR will be created for each module and part.

Previous section 2.1 Analysis set was re-numbered as 2.2

The paragraph has been modified to be specific how the efficacy analysis sets are classified: according to module, part, cohort or planned dose

Within Table 2 Deleted duplicate entry for *Best Objective response* in the efficacy data.

Restructured the sentence under endpoint 'Pharmacodynamics' as follows.

A new analysis set 'Evaluable for objective response set' is added.

A footnote [a] for the definition of measurable disease is added

A footnote [b] with the explanation that DLT analysis set will be derived from SRC meeting minutes is added.

A paragraph explaining how the patients will be selected for each analysis set, prior to data base lock is added.

Within Table 3 Added 'Evaluable for objective response' as an analysis set for efficacy endpoints except for progression free survival (PFS) and (OS).

Section 2.3 (previously section 2.2)

Added following sentence

The global pandemic (Covid-19) related important protocol deviations will also be captured and reported as per latest corporate standards

Changed 'with regard' to 'regarding'

Moved the following sentence from second paragraph of this section to the beginning of the third paragraph

The above list of protocol deviations is not exhaustive and additional important deviations will be added prior database lock as required.

Corrected patients 'skip a dose' to 'miss a dose'.

Corrected the second bullet point in such a way that missing a single safety assessment which having a potential implication to patient safety will be classified as important protocol deviation.

Based on section 9.4.3, PDc analysis will be presented in a separate document.

Section 3.1

Revised the data cut off specification as follows:

Data analysis will be performed separately for each module, study part or cohort, and a CSR may be written for each module separately.

Revised the entire section with an explanation to the reference date for safety analysis and efficacy endpoints.

Revised the Time Window table 4

Corrected 'half way' to 'halfway'

Corrected 'visit based' to 'visit-based'

Visit windowing for radiological tumour evaluations added.

Deleted the medical history, and tumour evaluations from the handling missing data section. The missing date won't be imputed for both medical history any tumour evaluations.

Section 3.2.1.1

added a ','

Section 3.2.1.3

Revised the title

Section 3.2.1.4

All casually related AEs are replaced with possibly related AEs as per AZ standard.

Section 3.2.15

Revised the to indicate the latest WHO dictionary standard will be used for the study summary reporting.

Section 3.2.1.6

AstraZeneca reference range for vital signs table added to the section.

Section 3.2.1.7

The list of laboratory safety variable table added.

Section 3.2.1.8 Added a new section for

Creatinine clearance formula added

The estimated Creatinine Clearance is will be calculated based on by using Cockcroft-Gault equation as follows.:

$CrCl = \{((140 - \text{age}) \times \text{weight}) / (72 \times SCr)\}$ Multiply by 0.85 (if patient is female)

CrCl (creatinine clearance) = mL/minute

Age = years

Weight = kg (the last weight measured closest to the time when serum creatinine is measured)

SCr (serum creatinine) = mg/dL

Section 3.2.1.9

Updated with the list of variables to be considered for physical examination summary tables.

Section 3.2.1.10

The AZ defined reference range for ECG variables added as Table 7.

Section 3.2.1.11

Revised the sentence as follows:

Change of left ventricular ejection fraction (LVEF) from baseline will be calculated at each scheduled post-baseline assessment time and summarised as follows.

Section 3.2.2.1

Added a new section 3.2.2.1 with tumour response criteria

Added a new paragraph as follows:

The modules require RECIST results, the RECIST tumour response data will be used to determine each patient's visit response according to RECIST version 1.1 as well as the mRECIST criteria. It will also be used to determine when a patient has progressed in accordance with RECIST and also their best objective response to study treatment.

Section 3.2.2.1.1

Expanded step 3 in TL visit responses subsequent to CR section follows:

If not all lesions meet the CR criteria (i.e., a pathological lymph node is selected as TL has short axis ≥ 10 mm or the reappearance of previously disappeared lesion) or a new lesion appears, then response will be set to PD.

Sentence corrected in Irradiated lesions/lesion intervention

If scaling up is not appropriate due to too few non-missing measurements, then the visit response will be set as NE.

Section 3.2.2.1.2

Changed title to Best Objective Response and added sub sections for RECIST and mRECIST Confirmation criteria for mRECIST PD is moved is added

Section 3.2.2.1.3

A separate section for Best Objective response rate criteria for mRECIST is added.

A sentence is added to the section to that mRECIST is applicable only to immune oncology combinations modules.

BoR will be assessed by mRECIST criteria as follows for immune oncology (IO) combination modules which may be added to the study in future.

The criteria for evaluating tumour response by mRECIST is elaborated with all conditions and scenarios.

Section 3.2.2.1.8

The following criteria added to overall survival endpoint.

OS analysis will be performed only for the part B of the study module.

Section 3.2.2.2

Revised the entire section as per AZ PK standards. Added each plasma and urine parameters required for AZD7846. Added the expansion and abbreviation of all parameters listed.

Diagnostic parameters are also included.

Added a section for plasma 4 β -hydroxy cholesterol.

Section 3.2.2.3 and 3.2.2.4

Deleted section for 'calculation or derivation of pharmacodynamic variables'

Section 4.2.5

Changed the abbreviation for pharmacodynamics to PDc (previously PD).

Section 4.2.1

Revised the sentence as follows:

The post-baseline results and it's change from baseline for laboratory, ECG, vital signs data at each timepoint will be summarised and presented using box plots globally for part A and for Part B of study

Section 4.2.2

Revised and added the following sentence:

A reference line at the -30% change in TL tumour size level, which corresponds with the definition of 'partial' response and another reference line at +20%, corresponds with the definition of 'progressive disease' will be added to the plots.

Section 4.2.3

Revised the entire section for Assessment of pharmacokinetic food effect

Changed the abbreviation for standard deviation to StD (previously SD).

Table 11 with list of descriptive statistics for each parameter required for PK part is added. Added a section for Plasma 4 β -hydroxy cholesterol summary requirements.

Section 6

Added the details of the new analysis set defined in this SAP as change in the analysis from protocol.

Version 3.0, 21 January 2022

Section 1.1

Updated with latest versions of protocol and electronic case report form.

The PK abbreviations and definitions are updated from those in the CSP in line with current AZ guidance for PK reporting

Table 4: visit windowing (safety analysis)

Updated the windowing for cycles greater than 3. Increased the analysis Day 1 analysis window from ± 1 to ± 2 .

Section 3.2.1.8 Creatinine Clearance

Added summaries to provided in addition to listings.

Section 3.2.1.9

This section is moved from 3.2.2.3 to 3.2.1.9

Previous section 3.2.1.9 re-numbered to section 3.2.1.10

Previous section 3.2.1.10 re-numbered to section 3.2.1.11

A correction was made as follows:

'summarised by visit and by actual treatment group' is replaced with 'summarised by module, by part, by cohort and visit'.

Previous section 3.2.1.11 re-numbered to section 3.2.1.12

A correction was made as follows:

Post baseline summaries by actual value, change from baseline and absolute change from baseline by categories as specified are added.

'summarised by visit and by actual treatment group' is replaced with 'summarised by module, by part, by cohort and visit'.

Previous section 3.2.1.12 re-numbered to section 3.2.1.13

Section 3.2.2.2

Plasma parameters, Urine parameters, and plasma diagnostic parameters are added by study module, by part, by cycle and day in a tabular form

Section 4.1

Added the following criteria for planned arm and actual arm:

The planned dose and the actual dose received by each patient will be closely assessed by study medical monitor and provided in a separate MS Excel sheet, which will be used for study summaries.

Section 4.2.3

Revised the entire section for Assessment of pharmacokinetic food effect

Changed the abbreviation for standard deviation to SD (previously StD).

Table 11 deleted

Replaced gStD with geometric standard deviation or gSD.

Replaced gCV with gCV%

The conditions for PK summary presentation for values > LLOQ replaced with language taken from AZ guidance document

Additional condition for one PK observation > LLOQ is added as follows:

One observation > LLOQ is presented as maximum with other summary statistics as NC.

Table 12 renumbered to Table 11.

Section 6

Language pertaining to addition of evaluable for objective response set for analysis was removed as it is specified in CSP version 5.0.

The PK parameter symbols re-defined in SAP to match with AZ Corporate CSRHLD Reporting Standard v 3.4 is added.

Section 7

Added list of references.

Version 4.0, December 2022

Grammatical, typographical, and formatting updates have been applied throughout the Statistical analysis plan.

Following the sponsor decision to halt development of AZ7648, the required number of tables, figures and listings were reduced to focus primarily on safety, with additional limited efficacy and PK outputs for publication purposes.

The following changes are made to the SAP with respect to the final scope the study.

All references to Part B of Core module, Part B expansion to Combination Module 1 and proposed food effect cohort in Core module were removed from analysis plan.

Removed following sections from previous version of the analysis plan.

- Best objective response by modified RECIST (mRECIST)

- Section 3.2.2.1.7 Overall survival

- Assessment of dose proportionality

- Assessment of Pharmacokinetic Food effect

- Interim analysis for Part B of the Combination module 1.

Section 1 Introduction : Updated the electronic case report form version to 9.1 (04 August 2022)

Section 2.2 Analysis set: Elaborated in detail how baseline and demographics, safety, pharmacokinetics and efficacy summaries been presented.

For consistency, all previous references to PK set/ PK analysis set were replaced with Pharmacokinetics set.

In the pharmacokinetics analysis sections, all references to ‘dose levels’ were replaced with ‘dose regimens’.

Section 4.2.1

Removed inclusion of box plots for ECG parameters.

Removed inclusion of the summary for 4 β -hydroxy cholesterol concentration data

Added a sentence to specify that the change from baseline in all haematological and chemistry parameters would be presented using spaghetti plot.

Removed tag from PK analysis since food effect cohort is not included in the study.

For consistency all ‘subjects/subject’ were replaced with ‘patients/patient’

1 STUDY OBJECTIVES

1.1 Introduction

This is a modular Phase I/IIa, open-label, multi-centre, study of AZD7648 administered orally, either as a monotherapy, or in combination with either cytotoxic chemotherapies or novel anti-cancer agents in patients with advanced malignancies. The modular design allows for an escalation of the dose of AZD7648 alone or in combination with either cytotoxic chemotherapies or novel anti-cancer agents, with intensive safety monitoring to ensure the safety of the patients.

This statistical analysis plan (SAP) provides the technical elaboration of the statistical analysis of safety, efficacy and pharmacokinetic (PK) data.

Following the sponsor decision to halt development of AZ7648, the required number of summary tables, figures and listings were reduced to focus primarily on safety, with additional limited efficacy and PK outputs for publication purposes.

The analyses described in this SAP are based upon the following study documents:

- Study protocol, Version 5.0 (1 October 2021).
- electronic Case Report Form (eCRF), D9170C00001 v 9.1 (04 August 2022).
- LDMS_001_00201968 Pharmacokinetic Evaluations in Clinical Studies.
- AZ Corporate CSRHLD Reporting Standards v3.4 (31 March 2021).

Specifications for tables, figures and listings are contained in a separate document.

1.2 List of modules

The following modules for the study are included within this SAP.

Core Module: AZD7648 Monotherapy. Part A, dose escalation

Combination Module 1: AZD7648 + PLD. Part A, dose escalation.

For the endpoints included in the safety, efficacy and exploratory objectives, see [Table 1](#).

Table 1 : Study objectives and endpoints

Primary objective (Safety):	Endpoint/Variable:
To investigate the safety and tolerability of AZD7648 when given orally to patients with advanced malignancies, as monotherapy and in combination with anti-cancer agents, and define	
 • Adverse events (AEs)/serious adverse events (SAEs) • Dose limiting toxicities (DLTs) • Physical examination

the doses and schedules for further clinical evaluation.
	
 • Eastern Cooperative Oncology Group performance status (ECOG PS) • Vital signs • Electrocardiogram (ECG) and Echocardiogram (ECHO; applicable for Combination Module 1 only) • Laboratory data

Secondary objectives:
	
Endpoint/Variable:

To characterise the PK of AZD7648, following a single dose and at steady state after multiple dosing, when given orally as monotherapy and in combination with anti-cancer agents.
	
 • Area under the curve to infinity (AUC_{inf}) and/or AUC_{last} after a single dose and AUC_∞ after multiple doses. • Maximum plasma concentration (C_{max}) after single and multiple doses. • Time to reach maximum plasma concentration (t_{max}) • Minimum plasma concentration at steady state (C_{min}) • Half-life (t_{1/2λz}) • Accumulation ratio (R_{ac}) • Dose proportionality (TCP) • AUC_{last} and C_{max} ratio for food effect (applicable for food effect cohort only in the Core module expansion phase) • Other PK parameters may also be estimated

^[a]To understand the cytochrome P450 3A4 (CYP3A4) induction potential of AZD7648
	
Post-dose to pre-dose 4β-hydroxy cholesterol ratio (only for AZD7648 Core Module)

To obtain a preliminary assessment of anti-tumour activity of AZD7648 as monotherapy and in combination with anti-cancer agents
	
Radiological response evaluated using response evaluation criteria in solid tumours (RECIST 1.1)
 
 • Percentage best change in target lesion (TL)

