3 OBJECTIVES AND ENDPOINTS

Primary objective:	Endpoint/Variable:							
To investigate the safety and tolerability of AZD7648	Adverse events (AEs)/serious adverse events (SAEs)							
when given orally to patients with advanced	DLTs							
malignancies, as monotherapy and in combination	Physical examination							
with anti-cancer agents, and define the doses and schedules for further clinical evaluation	Eastern Cooperative Oncology Group performance status (ECOG PS)							
	Vital signs							
	Electrocardiogram (ECG) and Echocardiogram							
	(ECHO; Combination Module 1 only)							
	Laboratory data							
Secondary objectives:	Endpoint/Variable:							
To characterise the PK of AZD7648, following a single dose and at steady state after multiple dosing, when given orally as monotherapy and in combination with anti-cancer agents. To characterise the effect of food on AZD7648 exposure (if conducted)	Area under the curve (AUC) and/or AUC_{0-t} after a single dose and AUC_{tau} after multiple doses. Maximum plasma concentration (C_{max}) after a single dose and $C_{max,ss}$ after multiple doses Time to reach maximum plasma concentration (t_{max}) Minimum plasma concentration at steady state ($C_{min,ss}$) Half-life ($t_{1/2}$)							
	Dose proportionality							
	AUC _{0-t} and C _{max} ratio for food effect							
To understand the cytochrome P450 3A4 (CYP3A4) induction potential of AZD7648	Post-dose to pre-dose 4-β-hydroxy cholesterol ratio							
To obtain a preliminary assessment of anti-tumour	Radiological response evaluated using response							
activity of AZD7648 as monotherapy and in	evaluation criteria in solid tumours (RECIST) 1.1							
combination with anti-cancer agents	• Percentage best change in target lesion (TL)							
	Duration of response							
	• Objective response rate (ORR)							
	• Progression-free survival (PFS)							
	• Overall Survival (OS) (Part B only)							

Table 2Study objectives

Tertiary/Exploratory objectives:	Endpoint/Variable:
	CCI
CCI	CCI CCI CCI
CCI	CCI

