9.4.3.1 PK Analyses

PK of AZD7648 is a secondary variable.

The PK Analysis Set includes patients who have reportable plasma concentrations and PK parameters and who have no important protocol deviations or AEs that may impact on PK.

Following single dose the following parameters maybe determined: C_{max} , time to reach maximum plasma concentration (t_{max}), terminal rate constant (λ_z), terminal half-life ($t_{1/2} \lambda_z$), area under the plasma concentration-time curve from zero to 24 hours (AUC₀₋₂₄), from zero to the time of the last measurable concentration (AUC_{0-t}) and from zero to infinity (AUC), apparent plasma clearance (CL/F), apparent volume of distribution ($V_{ss/f}$; $V_{z/f}$), mean residence time (MRT), renal clearance (CLR) and amount of drug excreted unchanged (Ae; % dose).

Following multiple dose (assuming SS conditions): Maximum plasma concentration at steady state ($C_{max,ss}$), time to C_{ss} max ($t_{max,ss}$), $C_{min,ss}$, area under the plasma concentration-time curve from zero to the end of the dosing interval (AUC_{ss}), apparent plasma clearance at steady state ($CL_{ss/f}$), extent of accumulation on multiple dosing (RAC), time dependency of the PK. Where possible other appropriate PK parameters may also be determined.

PK analysis of plasma concentration data for AZD7648 will be performed by AstraZeneca, or a CRO on behalf of AstraZeneca, using actual elapsed sampling times and standard Non Compartmental methods.

Statistical Analysis Methods for Assessment of Pharmacokinetic Food Effect

To evaluate the effect of food on the PK obtained after dosing with AZD7648 tablet, the primary PK parameters will be analysed using a linear mixed Effects model with treatment (fed/fasted) as a fixed effect and patient as a random effect to compare AUC0-t and Cmax in the fed state with AUC0-t and Cmax in the fasted state respectively. Log-transformation of exposure measurements (AUC0-t and Cmax) will be performed prior to analysis. The point estimate and 90% confidence interval (CI) for the ratio of geometric means for fed and fasted states will be provided. The food effect on a log scale (fed – fasted) and its upper and lower confidence limits will be exponentially back transformed to (and presented in) the linear scale. Further details will be provided in the SAP.

COMBINATION MODULE 1 – AZD7648 AND PEGYLATED LIPOSOMAL DOXORUBICIN

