Dose normalised C _{max}	Maximum observed plasma (peak) drug concentration divided by the dose administered (C _{max} /D)
Dose normalised AUC _{last}	Area under the plasma concentration-time curve from time zero to time of last quantifiable concentration divided by the dose administered (AUC _{last} /D)
Dose normalised AUC _{inf}	Area under the plasma concentration-time curve from time zero to infinity divided by the dose administered (AUC _{inf} /D)
Dose normalised AUC(0-12)	Area under the plasma concentration-time curve from time zero to 12 hours post dose divided by the dose administered (AUC(0-12)/D)
<hr/>	
Single dose Plasma PK Parameters (AZD7648 in combination with anti-cancer drug PLD):	
Combination escalation module, Part A, Cycle 1, Day 1	
<hr/>	
C _{max}	Maximum observed plasma (peak) drug concentration
t _{max}	Time to reach peak or maximum observed concentration or response following drug administration
t _{last}	Time of last observed (quantifiable) concentration
AUC(0-12)	Area under the plasma concentration-time curve from time zero to 12 hours post-dose
AUC _{last}	Area under the plasma concentration-curve from time zero to last quantifiable concentration
Dose normalised C _{max}	Maximum observed plasma (peak) drug concentration divided by the dose administered (C _{max} /D)

Dose normalised AUC _{last}	Area under the plasma concentration-time curve from time zero to time of last quantifiable concentration divided by the dose administered (AUC _{last} /D)
Dose normalised AUC _{inf}	Area under the plasma concentration-time curve from time zero to infinity divided by the dose administered (AUC _{inf} /D)
Dose normalised AUC(0-12)	Area under the plasma concentration-time curve from time zero to 12 hours post dose divided by the dose administered (AUC(0-12)/D)

Multiple dose Plasma PK parameters (AZD7648 alone):

Core escalation monotherapy module, Part A, Cycle 1 Day 8 or Visit Y

AZD7648 in combination with anti-cancer drug:

Combination escalation module, Part A, Cycle 1, Day 8

C _{max}	Maximum observed plasma (peak) drug concentration
t _{max}	Time to reach peak or maximum observed concentration or response following drug administration
t _{last}	Time of last observed (quantifiable) concentration
C _{avg}	Average drug concentration over a dosing interval
C _{trough}	Lowest observed plasma (trough) drug concentration reached before the next dose is administered

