AUC _τ	Area under the plasma concentration-time curve in the dosing interval τ (τ = CCI and τ = CCI)
AUC _{last}	Area under the plasma concentration-curve from time zero to last quantifiable concentration
CL/F	Apparent total body clearance of drug from plasma at steady state after extravascular administration
Dose normalised C _{max}	Maximum observed plasma (peak) drug concentration divided by the dose administered (C _{max} /D)
Dose normalised C _{trough}	Minimum observed plasma concentration divided by the dose administered (C _{trough} /D)

Dose normalised AUC _{last}	Area under the plasma concentration-time curve from time zero to time of last quantifiable analyte concentration divided by the dose administered (AUC _{last} /D)
-------------------------------------	--

Dose normalised AUC _τ	Area under plasma concentration-time curve in the dosing interval τ divided by the dose administered (AUC _τ /D)
----------------------------------	---

Rac AUC	Accumulation ratio for AUC, calculated by multiple dose AUC _τ /single dose AUC(0-12) (for CCI) or AUC(0-24) for CCI
---------	---

Rac C _{max}	Accumulation ratio for C _{max} , calculated by multiple dose C _{max} /single dose C _{max}
----------------------	--

TCP	Temporal change parameter in systemic exposure, calculated as multiple dose AUC _τ /single dose AUC _{inf}
-----	--

Single dose Plasma Diagnostic PK Parameters (AZD7648 alone):

Core escalation monotherapy module, Part A, Cycle 0, Day 1

AZD7648 in combination with anti-cancer drug:

Combination escalation module, Part A, Cycle 0, Day 1

λ_z lower	Lower (earlier) t used for λ_z determination
-------------------	--

λ_z upper	Upper (later) t used for λ_z determination
-------------------	--

$\lambda_z N$	Number of data points used for λ_z determination
---------------	--

λ_z span ratio	Time period over which λ_z was determined as ratio of $t^{1/2}\lambda_z$
------------------------	--

Rsq adj	Statistical measure of fit for the regression used for λ_z determination adjusted for the number of used data points ($\lambda_z N$)
---------	--

AUC _{extr}	Extrapolated area under the curve from t _{last} to infinity, expressed as percentage of AUC _{inf}
---------------------	---

Urine PK Parameters

Where data allow, the following parameters will be calculated for AZD7648 from the urine concentration data obtained from the Core escalation monotherapy module Part A on Cycle 0 Day 1 (CCI [REDACTED] cohorts) and Cycle 1 Day 8 (CCI [REDACTED]):

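### SAP Table 1 assigns dose proportionality to TCP, which measures change over time and can neither establish nor rule out proportionality between doses

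*SAP*

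**What the plan says.** **Endpoint.** Protocol Section 3 lists "Dose proportionality" as a secondary PK endpoint and names no parameter for it. SAP Table 1 (Section 1.2) carries the endpoint forward as "Dose proportionality (TCP" (closing bracket omitted).

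**What TCP is.** The SAP abbreviation list expands it as "Temporal change parameter in systemic exposure". Section 3.2.2.2 describes it as "Temporal change parameter in systemic exposure, calculated as multiple dose" AUCτ over single-dose AUCinf.

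**How the protocol treats change over time.** Section 9.4.3.1 names "time dependency of the PK" among the multiple-dose PK properties, separately from the dose-proportionality endpoint of Section 3.

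**What remains of a proportionality analysis.** The SAP version history for version 4.0 lists "Assessment of dose proportionality" among the removed sections. Section 4.2.3 now plans descriptive summaries of PK parameters by cohort (dosing regimen) and PK day, with no comparison between doses. Section 3.2.2.2 still derives dose-normalised Cmax, AUClast, AUCinf and AUC(0-12) for Cycle 0 Day 1; the AUCinf item is "Area under the plasma concentration-time curve from time zero to infinity divided by the dose administered". No sentence connects these to the endpoint. Section 6, on changes from the protocol, covers PK symbols and additional PK parameters and has no entry for dose proportionality.

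**The concern.** Dose proportionality asks whether exposure per unit dose is the same at different doses. TCP asks whether exposure at one dose is the same after repeated dosing as after a single dose. Table 1 names the second as the measure of the first, so the endpoint as written does not match the quantity assigned to it.

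The distinction matters for this drug. CYP3A4 induction potential is a secondary objective, and Table 5 of the protocol names CYP3A4 as the principal enzyme metabolising AZD7648. Auto-induction would lower TCP without any departure from dose proportionality. In Combination Module 1 there is a further complication. Full AUCinf is listed for Cycle 0 Day 1 (AZD7648 alone), while the multiple-dose parameters come from Cycle 1 Day 8, after PLD has been given. TCP there would also absorb any effect of PLD on AZD7648 exposure.

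At stake is what the CSR and any publication can say about proportionality, since the remaining PK outputs are kept for publication purposes.

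**Working it through.** The plan states no figure to reproduce; the check is on the definition.

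**Inputs**
- TCP = AUCτ (multiple dose) / AUCinf (single dose): SAP Section 3.2.2.2.
- Analyses use data from before any intra-patient dose escalation: SAP Section 4.1.
- Assumption: the Cycle 0 single dose equals each administered dose in Cycle 1. The readable text does not state this outright, because dose details are redacted. However, the accumulation ratios in Section 3.2.2.2 are not dose-normalised, which presupposes it.

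**Algebra.** Let F be bioavailability and CL clearance, with subscript 1 for the single dose and 2 for multiple dosing.
- AUCinf = F1 × D / CL1
- AUCτ = F2 × D / CL2
- TCP = (F2 / CL2) / (F1 / CL1); the dose D cancels.
- Dose proportionality requires AUCinf / D = F1 / CL1 to be the same at every D.

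The first contrast varies time at a fixed dose. The second varies dose at a fixed time.

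**Two-dose illustration**
- Doubling the dose triples AUC, with no change over time. Dose-normalised AUC differs by 3/2 = 1.5-fold, and TCP = 1.0 at both doses.
- Induction cuts AUC by 30% at every dose. TCP = 0.7 × AUCinf / AUCinf = 0.7, and dose-normalised single-dose AUC is identical at both doses.

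**Five-dose illustration.** The doses are 10, 20, 40, 80 and 160 in arbitrary units, not trial doses. All PK values are assumed.
- A: F = 0.2 × (D/10)^0.3, CL = 5, no change over time. At D = 10, AUCinf/D = 0.2/5 = 0.040. At D = 160, F = 0.2 × 16^0.3 = 0.459, so AUCinf/D = 0.459/5 = 0.092.
- B: F = 0.5, single-dose CL = 5, multiple-dose CL = 5/0.6. AUCinf/D = 0.5/5 = 0.100; AUCτ/D = 0.5 × 0.6/5 = 0.060.
- C: saturable elimination (V = 20, Vmax = 20, Km = 2), dosed every 24 h with almost complete washout between doses, by numerical integration.

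| Scenario | AUCinf/D, lowest dose | AUCinf/D, highest dose | Ratio | TCP at every dose |
|---|---|---|---|---|
| A: not proportional, stable over time | 0.040 | 0.092 | 2.3 | 1.0 |
| B: proportional, exposure falls 40% over time | 0.100 | 0.100 | 1.0 | 0.6 |
| C: not proportional, saturable elimination | 0.112 | 0.300 | 2.7 | 1.0 |

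A and C give an ideal TCP without proportionality; B gives a TCP well below 1 with exact proportionality. TCP can therefore mislead in either direction.

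**The case against.** The strongest reply is that this is one stray parenthesis in an objectives table. The sections that direct the work name and calculate TCP correctly as a temporal change. Table 1 also still shows a food-effect row, although version 4.0 took the food-effect cohort out of the plan, so incomplete clean-up is the likely cause. The removal of the formal assessment is disclosed in the version history and follows from the halt in development. No hypotheses are tested.

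Most of that stands, and it limits the size of the point. It does not remove it: Table 1 is where the SAP states its endpoints, the protocol row had no TCP in it, and Section 6 does not report the change.

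Three stronger readings are tempting, and the documents support none of them.
- *That TCP is the only relevant quantity reported.* Dose-normalised parameters are planned and summarised by dosing regimen, and Section 4.2.3 puts the geometric mean concentrations of all regimens on one plot. What is missing is the link to the endpoint.
- *That outputs will present TCP as evidence on proportionality.* Section 4 contains no such instruction, and the table and figure specifications are in a separate document that is not available here.
- *That TCP carries no information on non-linearity.* Saturable elimination with carry-over between doses can move TCP away from 1. Such a shift cannot be told apart from true time dependence, so it still does not measure proportionality.

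**Conclusion.** The point holds: Table 1 assigns the wrong parameter to the endpoint. This rests on the SAP's current definition and formula; the version history only explains how the row came to be left without an analysis. The algebra assumes that the single and repeated doses are equal within a regimen. The scenario figures show that the two properties can separate, not how AZD7648 behaves.

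The impact is modest. The endpoint is secondary and descriptive, the CSR is abbreviated, no dose decision in the SAP depends on it, and the data needed for a proper descriptive answer are already in the planned outputs. It should still be corrected before reporting, because the correction determines which results are read against the endpoint.

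**What to change.** 1. In SAP Table 1, list TCP on its own row as time dependency, matching protocol Section 9.4.3.1.
2. Then choose one of two options:
   - Keep dose proportionality and state in Section 4.2.3 that it will be described by comparing dose-normalised Cmax, AUClast and AUCinf on Cycle 0 Day 1 across dose regimens. Core Module cohorts run from 1 to 6 patients, and SAP Section 4.1 limits summaries with fewer than 3 patients to the count, minimum and maximum. Individual values should therefore be read alongside the summaries.
   - If proportionality is no longer assessed, remove the endpoint from Table 1 and record this in Section 6 as a change from the protocol.

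The cost is one table row and one sentence. Neither option needs new data or new derived parameters, because the dose-normalised values are already planned, listed and summarised.
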